$$\text{TWA-SaO}_2 = [(SaO_{2a} * \text{Time a}) + (SaO_{2b} * \text{Time b}) + \dots (SaO_{2z} * \text{Time z})] / (\text{Time a} + \text{Time b} + \dots \text{Time z})$$

We will build a multivariable regression model to test the association between TWA-PaO₂ and mRS at hospital discharge, adjusting for covariates previously demonstrated to be associated with poor neurological outcome after cardiac arrest. Covariates to be considered include: (1) pre-arrest comorbidities (Charlson index⁶⁹), (2) prolonged downtime (downtime > 20 minutes) (yes/no), (3) initial arrest rhythm (pulseless electrical activity/asystole vs. ventricular tachycardia/ventricular fibrillation), and (4) arrest location (in-hospital vs. out-of-hospital).⁷⁰⁻⁷⁵ In addition, in order to account for patients with lung injury (i.e. inability to maintain adequate oxygenation) we will add PaO₂/FiO₂ < 100mmHg (yes/no) to the regression model. We will build separate models to test the association between TWA-PaO₂ (adjusting for the five covariates above) and each of the five cognitive domains in our neuropsychological testing. We will then repeat these analyses using TWA-SaO₂ as the exposure variable of interest. This approach will not only allow us to test for an independent association between the exposure and neurological disability and neuropsychological deficits, but will also allow us to pinpoint one or more types of cognitive deficit (e.g. attention, executive function) most closely associated with the exposure. Given outcome measures that are quantitative (i.e. z-score for each cognitive domain) or semi-quantitative (i.e. mRS at hospital discharge), we will treat these outcomes as *continuous* dependent variables for modeling. Using continuous measures of the exposure and outcomes (rather than collapsing the data into categorical variables) will permit detection of subtle effects that could be missed if only categorical analyses were employed.

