Secondary analyses: We will compare proportions of good neurological outcome [defined as a mRS ≤ 3 (based on the preliminary data of our collaborator, [name], University of Pittsburgh)],⁴⁵ between subjects who receive the study intervention (i.e. rapid FiO₂ optimization) vs. those who do not receive the study intervention, using binomial test. Among survivors, we will compare the 180-day neuropsychological measures (composite z-scores for each cognitive domain) between the same two groups using t-test or Mann-Whitney U as appropriate with corrections for multiple comparisons. We will compare the proportions of patients able to return to work between the two groups using binomial test. We will compare plasma IsoPs/IsoFs at each time point between the two groups using t-test or Mann-Whitney U as appropriate with corrections for multiple comparisons.

Sample Size: The sample size calculation in the initial study proposal was based on the primary outcome, mRS at hospital discharge, and we planned to enroll a total of 266 subjects. To ensure adequate power to test the relationships between the above independent variables and cognitive domains, we assumed a medium relationship strength between the six independent variables and each of the five cognitive domains ($R^2 = 0.15$). In order to achieve 80% power and an $\alpha = 0.05$ we would require a minimal of 85 subjects to undergo neuropsychological testing at 180 days. This sample size will be among the largest prospective studies of

neuropsychological outcomes that we are aware of in the literature.^{8,29-32} Assuming a 15% drop out rate for lost to follow up for neuropsychological testing at 180 days we would require 98 subjects to be discharged with a mRS \leq 4. Based on preliminary data from REOX I we expect 35% of patients will be discharged with a mRS \leq 4 and undergo cognitive testing at 180 days. We would therefore require a minimal total sample size of 280 subjects between REOX I and II combined for the multivariable testing. We have enrolled 200 subjects in REOX I to date. We anticipate additional subjects to be enrolled in REOX I and therefore plan for 75 subjects to be enrolled in REOX II to ensure a total sample size of at least 280 subjects.

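### The domain-by-exposure cognitive regressions are meant to single out an affected domain but carry no multiplicity control, although the two-group tests of the same z-scores do

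*Combined protocol and SAP*

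**What the plan says.** Three parts of section D.2 bear on this.

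- **Analysis.** Separate models will "test the association between TWA-PaO₂ (adjusting for the five covariates above) and each of the five cognitive domains". The same set is then run with TWA-SaO2 as the exposure. The declared purpose is to "allow us to pinpoint one or more types of cognitive deficit (e.g. attention, executive function) most closely associated with the exposure". No multiplicity adjustment, testing order, global test, lead exposure or exploratory label is given for these models.
- **Secondary analyses.** The 180-day z-scores for the same five domains are compared between patients who did and did not receive the intervention, using "t-test or Mann-Whitney U as appropriate with corrections for multiple comparisons". The same wording is attached to the isoprostane and isofuran comparisons. No method of correction is named, and the wording does not reach the regressions.
- **Sample Size.** With six independent variables, R² = 0.15 for each domain, 80% power and alpha 0.05, the plan concludes that "we would require a minimal of 85 subjects to undergo neuropsychological testing at 180 days". It carries that number forward to 98 discharged survivors and 280 enrolled subjects.

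The Overview (D.1.2) lists the neuropsychological tests as secondary outcomes. The Specific Aims (D.1.1) make them Aim 3.

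**The concern.** A claim that one cognitive domain is affected is a selection from several tests. Five domains and two exposures give ten chances to find a nominally significant coefficient, and the plan has no rule that limits the overall error.

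The plan accepts the principle elsewhere, since it corrects the simple group comparisons of the same five z-scores. The adjusted models, which are the ones given the job of naming a domain, are left at 0.05 each. They are also the models from which the total of 280 is derived, so they are hard to read as informal exploration.

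At stake is how far a reader could rely on a reported domain-specific deficit. The planned sample size also says nothing about what a correction would cost in power.

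**Working it through.** **Inputs from the documents (D.2).** Five domains; two exposures; alpha 0.05; power 80%; six independent variables (the exposure and five covariates); R² = 0.15 per domain model; 85 tested; 15% loss; 35% of patients discharged with mRS ≤ 4 and tested.

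**Assumptions.** Sidedness is not stated, so I take two-sided tests of each exposure coefficient. No correlation among domains or between exposures is given. I use 0 to 0.7 between domains and 0 to 0.9 between exposures.

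**1. Reproduce the plan's figure.** Take the overall F test of a six-predictor regression, with f² = R²/(1 − R²) = 0.15/0.85 = 0.1765, noncentrality λ = f² × N, and degrees of freedom 6 and N − 7. At N = 85, λ = 15.0 and the critical F at 0.05 is 2.217, giving power 80.8%. The smallest N reaching 80% is 84. Then 85 × 1.15 = 97.75, rounded to 98, and 98/0.35 = 280. So the stated 85 is the size for a joint test of all six predictors, in one domain, at an uncorrected 0.05.

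**2. Familywise error, independent tests, no true association.**

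- Five tests: 1 − 0.95⁵ = 1 − 0.7738 = 22.6%.
- Ten tests: 1 − 0.95¹⁰ = 1 − 0.5987 = 40.1%.

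**3. Familywise error, correlated tests.** Multivariate-normal simulation with 400,000 draws. The correlation between two tests is the domain correlation times the exposure correlation.

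| Domain correlation | 5 tests | 10 tests, exposures 0 | 10 tests, exposures 0.5 | 10 tests, exposures 0.9 |
|---|---|---|---|---|
| 0 | 22.6% | 40.2% | 37.8% | 30.5% |
| 0.3 | 20.9% | 37.4% | 35.3% | 28.3% |
| 0.5 | 18.3% | 33.3% | 31.1% | 24.7% |
| 0.7 | 14.9% | 27.5% | 25.5% | 20.1% |

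(The 40.2% is the simulated value of the exact 40.1%.) For domain correlations of 0.3 to 0.7 the range is about 15-21% for five tests and 20-37% for ten. Over the whole table the error runs from 14.9/5 ≈ 3 to 40.1/5 ≈ 8 times the nominal 5%.

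**4. What a correction does to the plan's own power figure.** Bonferroni over five domains gives 0.05/5 = 0.01. At N = 85 the critical F rises to 3.042 with λ still 15.0, and power for the same overall F test falls from 80.8% to 58.8%.

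**5. What that figure does not cover.** The domain claim rests on the exposure coefficient, a 1-df test. Its power depends on the share of variance that the exposure explains beyond the covariates, which the plan does not give. For illustration, at N = 85 with total R² = 0.15 and noncentrality N × (unique R²)/0.85:

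| Assumed unique R² | Power at 0.05 | Power at 0.01 |
|---|---|---|
| 0.02 | 29% | 12% |
| 0.05 | 60% | 35% |
| 0.10 | 88% | 70% |

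**The case against.** The strongest case on the other side has four parts.

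- **The outcomes are secondary.** The primary outcome, mRS at discharge, is unaffected, and the design is a non-randomised comparison with an earlier observational cohort. Strict familywise control is not the only defensible choice. This stands: an explicit exploratory label would also be adequate. The plan gives no such label, and the pinpointing aim points the other way.
- **The tests are not independent.** They use the same survivors and two oxygenation measures from the same 24 hours, so 40.1% is an upper figure. This stands too. A reader might infer that a false domain finding is likely; the numbers do not support that. The risk is below one half in every scenario examined, and all of them assume no true association in any domain.
- **The power figures belong to another hypothesis.** A reader might take 59% as the corrected power to detect an oxygen-domain association. It is not. Both 80.8% and 58.8% describe the joint six-predictor test. Power for the TWA-PaO2 coefficient cannot be derived from the documents and could be well above or below either figure.
- **A correction alone does not deliver the aim.** Neither Holm nor ranking p-values shows that one domain is more closely associated than another. Gating on the mean of the five z-scores could block an effect confined to one or two domains. Section C.3.7 reports deficits concentrated in two domains, so that cost is a real possibility. I therefore do not recommend the gate.

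None of these supplies the missing rule.

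**Conclusion.** The concern holds as an unaddressed multiplicity problem in a secondary analysis. Run as written, the ten regressions carry a familywise error of about 20-40%, and the five TWA-PaO2 models alone about 15-23%, if no domain is truly associated. The ends of those ranges depend on correlations that the documents do not give; the exact independent-test values are 22.6% and 40.1%.

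The plan is also inconsistent: it corrects the unadjusted comparisons of the z-scores but not the adjusted models that are to name a domain. The quoted 80% power is for one uncorrected overall domain model. It does not speak to the exposure coefficient, with or without correction.

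The documents do not support reading this as a threat to the primary result, or as showing that a false domain claim is more likely than not. The change should be made, because without it a nominally significant domain could not be relied on as the affected one.

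**What to change.** Amend the SAP wording in one of two ways.

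1. **Controlled.** Name TWA-PaO2 as the lead exposure. Apply Holm across its five domain coefficients, which extends the plan's own principle from the Secondary analyses paragraph. Report the TWA-SaO2 models as supportive, with estimates and confidence intervals and no significance claims.
2. **Exploratory.** Label all ten models exploratory, report estimates and intervals, and remove the statement that they will pinpoint a domain.

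Under either option, claim that one domain is more closely associated than another only from a direct comparison of the domain effects. In the Sample Size paragraph, state that the 80% refers to the overall six-predictor test in a single domain model at an uncorrected 0.05.

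**Cost.** Option 1 lowers power for individual domains. Holm starts at 0.01 for the smallest p-value and relaxes from there, so it is never less powerful than Bonferroni. Option 2 gives up the confirmatory claim. Neither adds patients or changes data collection, and the primary outcome is unaffected.

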C.3.7. Neuropsychological deficits among survivors of out-of-hospital cardiac arrest.

[figure not shown]

This NIH-funded (R01HD046442) prospective study determined the nature and severity of residual cognitive deficits for survivors of OHCA. Thirty OHCA patients who recovered alertness within 1-3 days of ROSC but remained confused at one week, and 30 non-OHCA coronary care admissions (matched controls) were administered neuropsychological testing at 90 days in five cognitive domains: memory, executive function, lexical-semantic, visuoperceptual, and psychomotor (**Figure 8**). Subjects fell into two deficit profiles. Two-thirds had only mild memory deficits and borderline psychomotor deficits compared to controls; 40% in this mild group had returned to work. The other one-third of patients had severe impairments in all domains. In the severe group, only as impairment in memory or psychomotor

domains increased did impairments in other domains appear. Follow-up evaluation at one year revealed discouraging little further cognitive improvement over the levels reached at 90 days. Only one additional subject returned to work. In addition, we assessed health-related quality of life (QOL) at one year using the Sickness Impact Profile-68 (SIP-68)⁴⁴, a measure of health-related functional status in rehabilitation medicine, and found that the OHCA patients reported more adverse effects on health than the cardiac control patients due to poorer psychological health and social participation, not due to effects on physical health.

The proposed study will use a similar methodology for neuropsychological testing and functional assessment at 180 days after resuscitation among survivors.

Figure 8: Composite z-scores – mean and standard deviation – for neuropsychological function in five cognitive domains among cardiac controls (CC), all out-of-hospital cardiac arrests (OHCA), and mild and severely impaired OHCA patients separately. Deficits after OHCA were most common and most severe in memory and psychomotor domains.

D.1. RESEARCH DESIGN AND METHODS

D.1.1 Specific Aims

We will test if a protocol for rapid FiO₂ optimization following ROSC from cardiac arrest is associated with:

- *Reduced in vivo oxidative stress during the post-resuscitation phase of therapy (Aim 1)*

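### Five separate regressions are meant to identify the cognitive domain most tied to oxygen exposure, but the plan never compares the exposure slopes between domains

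*Combined protocol and SAP*

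**What the plan says.** In D.2, Analysis, the cognitive outcomes are handled one at a time: "We will build separate models to test the association between TWA-PaO₂ (adjusting for the five covariates above) and each of the five cognitive domains". The set is then run again: "We will then repeat these analyses using TWA-SaO₂ as the exposure variable of interest". That makes ten domain models. The outcomes are continuous ("i.e. z-score for each cognitive domain"). The inference drawn is that this approach can "pinpoint one or more types of cognitive deficit (e.g. attention, executive function) most closely associated with the exposure".

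The Sample Size paragraph assumes an R² of 0.15 for six independent variables in each of the five domains and arrives at 85 patients tested at 180 days for 80% power at α = 0.05. Correction for multiple comparisons is stated under Secondary analyses for the two-group comparisons, but not for these regressions. The plan describes no joint model of the five scores, no exposure-by-domain term, no test of equal slopes and no interval for a difference between domains.

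**The concern.** Saying that one domain is more strongly linked to exposure than another is a statement about the difference between two slopes. Five separate models each test one slope against zero. If attention reaches p < 0.05 and reasoning does not, the two slopes may still be equal. If the slopes are ranked instead, one must come out largest even when all the true slopes are the same. Adjusting the five p-values does not help, because the quantity tested is still each slope against zero.

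At stake is the interpretation of Aim 3. A report that oxygen exposure harms one type of cognition in particular could rest on sampling variation around a shared effect, and the planned output would give a reader no means of telling the two apart.

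**Working it through.** **1. The plan's own figure.** For the overall F test of six predictors, f² = R²/(1 − R²) = 0.15/0.85 = 0.1765. With n = 85, λ = 85 × 0.1765 = 15.0 on 6 and 78 df, and power is 80.8%. The smallest adequate n is 84 (80.2%), so the stated 85 reproduces to within one patient. It powers the joint contribution of six variables within one domain. It does not power the exposure coefficient or a contrast between domains. If the exposure held an equal sixth of the R² (0.15/6 = 0.025), then λ = 85 × 0.025/0.85 = 2.5 and power for its coefficient would be about 35%.

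**2. How often the five results split when the true effects are identical.**
- From the documents: n = 85, six predictors (78 residual df), total R² 0.15, five domains, α = 0.05.
- Assumed, because the documents give neither: the exposure's unique R², and a common residual correlation between domains.
- A split means at least one domain is significant and at least one is not. For independent domains with power π the probability is 1 − π⁵ − (1 − π)⁵. At π = 0.5 this is 1 − 2/32 = 94%. With correlated domains it was simulated, at 4,000 to 5,000 trials per setting with predictors drawn at random.

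| Unique R² of exposure | Power, one domain | Split at correlation 0.3 / 0.5 / 0.7 |
|---|---|---|
| 0.025 | about 0.35 (formula in step 1) | 73% / 60% / 47% |
| 0.05 | about 0.56 | 77% / 66% / 51% |
| 0.085 | about 0.78 | 56% / 49% / 37% |
| 0.15 | about 0.97 (same formula) | about 13 to 18% over the three |

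Repeat runs moved cells by a point or two, so the 0.05 and 0.085 rows together span about 37 to 79%. Treating the predictors as fixed (noncentrality n·f²) lowers the last row to 13% / 11% / 9%. Holm adjustment across the five domains still left splits in 23 to 61% of simulated trials.

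**3. The direct comparison on the same data.** A Hotelling-type test that the five exposure slopes are equal (4 numerator df) rejected in 4.6 to 5.3% of trials with identical effects, as it should at α = 0.05.

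**4. Ranking instead of p-values.** With identical effects, the median gap between the largest and smallest standardized slope was 0.13 (correlation 0.7) to 0.20 (correlation 0.3). The true standardized slope is √(0.05/0.85) = 0.243 or √(0.085/0.85) = 0.316. The chance gap is therefore between 0.13/0.316 = 41% and 0.20/0.243 = 82% of the slope itself.

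**5. What a joint analysis can and cannot do at n = 85** (assumed scenarios, correlation 0.3 / 0.5 / 0.7).
- One domain affected (unique R² 0.085), four unaffected: a test of the slope common to all five has power 0.14 / 0.11 / 0.10, against 0.78 for that domain's own model.
- One domain at 0.085, four at 0.02: the common-slope test has power 0.68 / 0.55 / 0.47, again below 0.78. The test of unequal slopes has 0.19 / 0.24 / 0.42.

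**The case against.** The plan never says that a domain will be singled out because it is significant while another is not. The outcomes are z-scores, so slopes can be set side by side, and the sentence allows for more than one domain. This stands. A reader might infer that 37 to 79% is the trial's error rate, or that the trial will report selective injury. The documents support neither: the split rule is one possible reading, the inputs behind the range are assumed, and many simulated trials show no split at all. What survives is narrower. Ranking slopes without an interval for their difference does not show that they differ either (step 4).

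A reader might also take C.3.7 as evidence for one effect shared by all domains, since it reports: "The other one-third of patients had severe impairments in all domains". The same section says that the other two-thirds had mainly mild memory and borderline psychomotor deficits. Its battery also differs from the one planned here, and deficits that occur together say nothing about whether exposure slopes are equal. Shared and selective effects both remain open.

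Nor should a common-slope test be read as the most powerful option or as a gate before the domain models. It gains power only when effects are similar across domains; under selective injury it loses badly (step 5).

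Finally, softer wording alone would remove the contradiction. That is a fair minimum, but it gives up a question the plan says it will answer and could address with data already collected.

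**Conclusion.** The gap is real. The plan states a between-domain conclusion and specifies no between-domain comparison, so the analysis as written cannot support it. This follows from the text and does not depend on the simulation.

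The size is illustrative. With identical true effects, results split in about 37 to 79% of trials for an exposure-specific R² of 0.05 to 0.085 and residual correlation of 0.3 to 0.7. The figure is about 13 to 18% if the exposure alone carries 0.15, and above 90% for independent domains at 50% power. The documents do not say where in this range the trial lies. The 85 patients were sized for six predictors within one domain, so no assurance about a between-domain contrast can be drawn from the sample-size paragraph.

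The per-domain association tests remain valid for their own question. The point touches one inference on a secondary outcome and leaves the primary mRS analysis alone. It is a cheap improvement.

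**What to change.** Keep the five separate models as the tests of association within each domain. Add, for each exposure, one joint model of the five z-scores (multivariate regression, or a mixed model with unstructured covariance) with the same five covariates. Report between-domain differences in exposure slope with confidence intervals, and an exposure-by-domain test. State in advance that a domain will be described as the one most strongly linked to exposure only if that comparison supports it; otherwise present the five slopes descriptively. A common-slope estimate may be added as a supplement, but it must not decide whether the domain models are read.

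The cost is a few lines in the Analysis section and one extra model per exposure, with no new patients, visits or measurements. The downside should be stated openly: at 85 patients the exposure-by-domain test has power of only about 0.2 to 0.4 in the graded scenario above, so domain-specific claims will be harder to make and a non-significant result will not show that the slopes are equal. If the sponsor does not want the extra model, the sentence about pinpointing a domain should be withdrawn.
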